STU#: 00213159

PROTOCOL TITLE:

Home-based physical therapy intervention to decrease frailty in liver transplant candidates

PRINCIPAL INVESTIGATOR:

[name], MPH
Associate Professor of Surgery
Department of Surgery-Division of Organ Transplantation
Work [contact]
[contact]
Email Address: [contact]

VERSION DATE: 11/9/21, Version 1.3

NCT04836923

STUDY SUMMARY:

Investigational Agent(s) (Drugs or Devices)	N/A
IND / IDE / HDE #	N/A
Indicate Special Population(s)	 Children  Children who are wards of the state  Adults Unable to Consent  Cognitively Impaired Adults  Neonates of Uncertain Viability  Pregnant Women  Prisoners (or other detained/paroled individuals)  Students/Employees
Sample Size	500
Funding Source	None
Indicate the type of consent to be obtained	 Written  Verbal/Waiver of Documentation of Informed Consent  Waiver of HIPAA Authorization  Waiver/Alteration of Consent Process
Site	 Lead Site (For A Multiple Site Research Study)  Data Coordinating Center (DCC) *All data will be collected at NMH
Research Related Radiation Exposure	 Yes  No
DSMB / DMC / IDMC	 Yes  No

OBJECTIVES:

Frailty is a significant problem in patients undergoing liver transplant and is associated with poor outcomes and survival. Hence, optimizing physical fitness and counteracting frailty is important. However, many interventions are very resource intensive and therefore not feasible.

In this study, we aim to test the effectiveness of a newly designed intervention to improve frailty in liver transplant candidates. The “Liver FrailTy” intervention (LIFT) will consist of an evaluation by a physical therapist, an individualized home exercise prescription (HEP), exercise tracking using a smart phone application, daily text reminders to exercise and recurrent telephone check-ins. We also aim to perform “Realistic Effort Action Planning” (REAP), which is a form of personality-informed motivational interviewing, in a subset of patients to determine if this enhances the LIFT intervention.

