Our central hypothesis is that our LIFT (+/- REAP) intervention will 1) improve adherence to recommended levels of exercise in end-stage liver disease 2) reduce pre-transplant frailty and 3) will improve pre- and post-transplant clinical outcomes.

STUDY ENDPOINTS:

Primary endpoints:

- Frailty (measured by Liver frailty index [LFI])
- Clinical outcomes: placement on LT waitlist, waitlist-mortality, post-transplant mortality, post-transplant disposition (acute rehabilitation, subacute rehabilitation center, home, etc), number of hospitalizations, duration of hospitalizations, liver related complications (ascites, hepatic encephalopathy, variceal bleeding, hepatorenal syndrome, hepatopulmonary syndrome, infections).
- Feasibility (measured by 8-question emailed survey)

[figure not shown]
Secondary endpoints:

- Endurance (measured by the 4-meter walk test).
- Patient adherence to the home exercise prescription (measured by daily diary counts of adherence to prescribed exercises, tracked on the TrueCoach application)
- Degree of hepatic encephalopathy (measured by List Sort Working Memory [LSWM] test and the Flanker Inhibitory Control and Attention [FICA])
- Patient-reported quality of life (measured by various PROMIS questionnaires)
- Feasibility/acceptability (measured by a study-specific questionnaire evaluating the acceptability and feasibility as reported by patients, providers and support staff)

STUDY INTERVENTION(S) / INVESTIGATIONAL AGENT(S):

Home exercise prescription (HEP) detailed below in study design.

PROCEDURES INVOLVED:

Recruitment for Quality of Life Assessment Study:

- A Northwestern Medicine Enterprise Data Warehouse (NMEDW) search will be used to identify all patients who have been seen in Transplant Evaluation Clinic and are currently being considered for liver transplantation or are already on the waitlist or have received a transplant.
- Alternatively, a list of the patients described above will be obtained from the transplant coordinator.

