- *Videoconference/telephone check-in (every 1 week)*
 - Performed by a member of the research team.
 - If patients are unable to track adherence to exercise regimen via TrueCoach application, the team member will document daily physical activity on this call.
 - If patients have questions regarding exercise regimen, they will be contacted by a physical therapist.
 - Progress reviewed and exercise regimen potentially adjusted by physical therapist based on data collected and patient experience.
 - REAP follow up (time: 5-15 minutes):
 - Reflect with patient on previous action plan and level of realistic sustained effort put forward in the past week.

- Encourage patient to adjust action plan according to perceived threshold of sustained effort.
- *Clinical data collection via NEDW and review of EMR (every 4 weeks)*
 - Number of hospitalizations, intensive care unit admissions, duration of hospitalizations, development of decompensating events (ascites, hepatic encephalopathy, variceal bleeding), transplant status, type of LT (living donor LT, simultaneous liver-kidney), duration of hospital admission for LT, duration of ICU admission for LT, duration of intubation post-LT, post-transplant discharge disposition, date of death, cause of death, post-transplant complications (rejection, infection, biliary complications).
- *Clinic visits (every 3 months, same tools as noted above)*
 - Patient-reported quality of life assessment
 - Hepatic encephalopathy assessment
 - Frailty assessment, 4-meter walk test
 - Physical therapy in person update
- Feasibility assessment (for those who remain in the study for atleast 1 month or until receiving a liver transplant; surveys emailed)
 - Tool: 8-question survey emailed to eligible subjects as noted above.
 - Data collected via REDCap.
 - Time: < 3 minutes
 - Appendix G

Audio/Video Recording:

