All telephone calls and videoconference calls between team members and patients will be recorded. Recording will be necessary to ensure standardization of follow up communications. This is critical in the pilot study to eliminate confounding factors between the LIFT and LIFT+REAP subgroups. Only IRB approved personnel will have access to the data. All data will be stored on FSM shared drive-accessed only by approved personnel. All data is accessed through password protected computer kept in locked offices. All patient identifiers will be stored in a separate password protected file. All recordings will be deleted within 3 years of study completion.

Retrospective Control group for those who enroll in the PT intervention study:

- A list of all patients who were evaluated for liver transplantation at Northwestern Memorial Hospital from January 1st 2018 through October 26th, 2020 will be drawn from the EDW.
- Baseline Clinical data will be collected via the EDW and via chart review. Data will include: Age, gender, race, ethnicity, body mass index (BMI), employment status, education, marital status, etiology of liver disease, complications of liver disease (ascites, hepatic encephalopathy, presence of esophageal/gastric varices, history of variceal bleeding, hepatorenal syndrome, hepatopulmonary syndrome), medical history (coronary artery disease, chronic kidney disease, dialysis dependence, hypertension, hyperlipidemia), and baseline laboratory data (platelets, serum sodium, serum creatinine, PT/INR, total bilirubin, albumin, calculated MELD). No data will be collected that is not already existing in the EMR at the date of IRB submission.
- Follow up data will be extracted retrospectively from the EDW and via chart review. Follow up data will include: Number of hospitalizations, intensive care unit admissions, duration of hospitalizations, duration of intensive care unit admission, development of decompensating

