- events (ascites, hepatic encephalopathy, presence of esophageal/gastric varices, history of variceal bleeding, hepatorenal syndrome, hepatopulmonary syndrome, infections), transplant status, date of death, cause of death, placement on LT waitlist, delisting from LT waitlist, date of transplant, type of LT (living donor LT, simultaneous liver-kidney), duration of hospital admission for LT, duration of ICU admission for LT, duration of intubation post-LT, post-transplant discharge disposition, post-transplant complications (rejection, infection, biliary complications, hypertension, hyperlipidemia, liver frailty index scores, Karnofsky Performance Status Scores, body mass index (BMI), and laboratory data (platelets, serum sodium, serum creatinine, PT/INR, total bilirubin, albumin, calculated MELD). No data will be collected that is not already existing in the EMR at the date of IRB submission.
- A waiver of consent will be requested for this retrospective EDW data extraction. It meets criteria for a waiver of consent as listed on the IRB website: 1) The research is not FDA regulated. 2) The research does not involve non-viable neonates. 3) The research involves no more than minimal risk to subjects. 4) The waiver or alteration will not adversely affect the rights and welfare of the subjects. 5) The research could not be practicably carried out without the waiver. Patients will not be required to complete any tasks as part of the control study and will not be subject to any risks. Seeing as there are approximately 300 patients who have received a liver transplant at Northwestern since 1/2018, it would be impractical to consent each patient. Moreover, many patients have passed away or likely no longer follow up closely at Northwestern. Obtaining consent from these deceased patients would be impossible and obtaining consent from patients who no longer follow at NMH would be very difficult. Although consent could be obtained from deceased patients' families, this could adversely affect the rights of privacy for these families and cause more emotional harm. 6) The research could not be carried out without using private information in an identifiable format. 7) Whenever appropriate, the subjects will be provided with additional pertinent information after participation.

Participants who enroll in the Quality of Life Assessment Study:

Baseline session:

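### Hospitalisations and deaths come only from Northwestern records, and no last-contact date, person-time or censoring rule covers time those records cannot see

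*Combined protocol and SAP*

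**What the plan says.** Under STUDY ENDPOINTS the primary clinical outcomes include "waitlist-mortality, post-transplant mortality, post-transplant disposition" and "number of hospitalizations, duration of hospitalizations". The hospitalisation endpoints are a number and a duration, with no time base.

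The sources are as follows.

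- **Site.** The STUDY SUMMARY notes that "All data will be collected at NMH".
- **PT arms.** Both follow-up lists under PROCEDURES INVOLVED give the same source: "Clinical data collection via NEDW and review of EMR (every 4 weeks". A weekly call is listed for both arms. Its stated content is exercise tracking, questions, progress and (in one arm) REAP. The section on safety monitoring adds falls and strains. Hospital stays are not listed.
- **Controls.** The group is defined from "A list of all patients who were evaluated for liver transplantation at Northwestern Memorial Hospital from January 1st 2018 through October 26th, 2020". On outcomes, "Follow up data will be extracted retrospectively from the EDW and via chart review", with the limit that "No data will be collected that is not already existing in the EMR at the date of IRB submission".
- **Expected loss.** The waiver paragraph, repeated under CONSENT PROCESS, says that "many patients have passed away or likely no longer follow up closely at Northwestern".

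The Statistical analysis section plans chi-squared and t-tests between LIFT and LIFT + REAP, and a survival analysis without a time origin or censoring rule. It contains no analysis against the controls. STUDY TIMELINES sets the follow-up of PT participants (to 1 year after transplant, or at most 5 years if not listed) but not that of controls.

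**The concern.** A single centre's record shows an admission or death elsewhere only if word of it reaches that chart. The sponsor uses loss of contact among controls to justify the waiver but does not carry it into the outcome data. A raw count per patient, or a yes/no outcome, treats a patient who left after six months like one observed throughout with no further events.

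Both randomised arms receive LIFT, so the retrospective group is the only comparison without it, and Aim 4 asks about the effect of LIFT on these outcomes. PT participants have weekly calls and three-monthly visits, so their records may well be more complete. If so, controls would look healthier than they were and a benefit of LIFT would be understated. In the randomised comparison, admissions missed in both arms are events lost from a primary endpoint.

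**Working it through.** **No planned figure to reproduce.** The plan gives no loss rate, event rate or follow-up length for controls. Its one design figure, a sample of 500, comes without alpha, power or effect size and has no bearing here. Every numerical input below is an assumption.

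**1. Control hospitalisation rate.** Let L be the share of controls who leave and U the share of their follow-up that is unseen and scored as zero events.

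- Observed/true control rate = 1 − L × U
- Apparent LIFT/control rate ratio = true ratio / (1 − L × U), if PT capture is complete

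| L | U | Control rate too low by | Ratio shown if truth is 1.00 | Ratio shown if truth is 0.75 |
|---|---|---|---|---|
| 30% | 25% | 7.5% | 1.08 | 0.81 |
| 30% | 50% | 15% | 1.18 | 0.88 |
| 50% | 25% | 12.5% | 1.14 | 0.86 |
| 50% | 50% | 25% | 1.33 | 1.00 |

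Over a wider range, the understatement runs from 2.5% (L = 10%, U = 25%) to 37.5% (L = 50%, U = 75%).

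**2. Control mortality.** Assume a true one-year mortality of 20%, a constant hazard, and no deaths seen after leaving. Observed mortality = (1 − L) × 0.20 + L × (1 − 0.80^(1−U)). In the table's order this gives 18.6%, 17.2%, 17.7% and 15.3%.

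**3. Dependence on PT capture.** If shares e(PT) and e(C) of admissions occur elsewhere and never reach the chart, the apparent ratio is the true ratio × (1 − e(PT)) / [(1 − e(C)) × (1 − L × U)]. Equal shares cancel and leave the table as it stands. With e(PT) = 10%, e(C) = 0 and L × U = 7.5%, the multiplier is 0.90/0.925 = 0.97, so the direction turns round.

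**4. Randomised arms.** If a share e of admissions is missed equally in both arms, the rate ratio is unchanged. Under a Poisson model the standard error of its logarithm grows by 1/√(1 − e). For an assumed e of 10% to 40% that is 1/√0.9 = 1.05 to 1/√0.6 = 1.29.

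**5. Effect of a person-time denominator.** Take L = 30%, U = 50% and an assumed 1.5 admissions per patient-year. The raw mean is 1.5 × (0.70 + 0.30 × 0.50) = 1.275, which is 15% too low. Observed person-time is 0.85 years per patient, and 1.275/0.85 = 1.50. This recovery holds only if leaving is unrelated to risk.

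**The case against.** The strongest reply is that the plan is silent and does not prescribe an error. A reader might infer that it counts unseen time as event-free. No sentence says so, and the planned survival analysis could censor at last contact. That stands: the scoring is the default of the stated count and yes/no tests, not a written rule.

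A reader might also infer that the protocol reports that many controls have left. The sentence joins deaths with patients who only likely no longer follow closely, and gives no share for either. It follows a remark about roughly 300 transplant recipients, whereas the controls are all patients evaluated. Some deaths are evidently known to the team and are captured events. This stands too. It is why the size is unknown, but it does not supply a rule for those who did leave.

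The limit to data in the EMR at IRB submission bounds unseen time. It is a data cut-off, however, and does not identify when each patient was last observed.

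A third tempting reading is that a real LIFT benefit will be hidden or reversed. No comparison with controls is written, and the direction depends on relative capture (step 3), so the documents do not support it. Nor do they support a directional bias between the randomised arms, which share the same four-weekly source and weekly call.

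Finally, the call content is only outlined, and Appendices A and B, which list the extracted variables, are not in the text available here. A call item or a last-contact date may exist. If so, the protocol should say how it is used.

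**Conclusion.** The gap is real and worth closing. One centre's records are the only described source for primary endpoints, the protocol itself expects incomplete contact with controls, and nothing defines observed time.

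For LIFT against controls, control events may be understated if capture in the PT arms is more complete. The 7.5% to 25% range rests wholly on assumed losses, and on the raw-count and yes/no methods written for the randomised arms being carried over to the controls. For LIFT against LIFT + REAP, the consequence is mainly fewer observed events and wider intervals.

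**What to change.** 1. **Randomised arms.** On the existing weekly call, ask both arms in the same words about any hospital stay since the last call, where and on what dates. Use the answers with the record data in the LIFT vs LIFT + REAP comparison.
2. **Hospitalisations in any comparison with controls.** Use record-based events only in both groups, so that the call does not add events on one side. Extract the date of last Northwestern contact, defined in the same way from the records for both groups, and analyse rates per observed person-time. End time at transplant only for pre-transplant endpoints. Start post-transplant endpoints at transplant, because stopping everyone there would discard post-transplant mortality and disposition, which are primary.
3. **Mortality in that comparison.** Apply one last-contact censoring rule to both groups and count deaths only within the observed window or a common window. Censoring survivors early while counting every known later death would inflate mortality. Add a sensitivity analysis in which departure is related to risk.

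The cost is one more call item, one more date in an extraction already planned, and somewhat less control person-time. An external vital-status source would strengthen item 3, but it would need a change to the stated limit on control data.

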 - If patients have questions regarding exercise regimen, they will be contacted by a physical therapist.
 - Progress reviewed and exercise regimen potentially adjusted by a physical therapist based on data collected and patient experience.
- *Clinical data collection via NEDW and review of EMR (every 4 weeks)*
 - Number of hospitalizations, intensive care unit admissions, duration of hospitalizations, development of decompensating events (ascites, hepatic

encephalopathy, variceal bleeding), transplant status, type of LT (living donor LT, simultaneous liver-kidney), duration of hospital admission for LT, duration of ICU admission for LT, duration of intubation post-LT, post-transplant discharge disposition, date of death, cause of death, post-transplant complications (rejection, infection, biliary complications).

- *Clinic visits (every 3 months, same tools as noted above)*
 - Patient-reported quality of life assessment
 - Hepatic encephalopathy assessment
 - Frailty assessment, 4-meter walk test (standard of care)
 - Physical therapy in person update (standard of care)
 - Data collection via NMEDW extraction and chart review: Number of hospitalizations, intensive care unit admissions, duration of hospitalizations, development of decompensating events (ascites, hepatic encephalopathy, variceal bleeding), transplant status, type of LT (living donor LT, simultaneous liver-kidney), duration of hospital admission for LT, duration of ICU admission for LT, duration of intubation post-LT, post-transplant discharge disposition, date of death, cause of death, post-transplant complications (rejection, infection, biliary complications).
- Feasibility assessment (for those who remain in the study for at least 1 month or until receiving a liver transplant; surveys emailed)
 - Tool: 8 -question survey emailed to eligible subjects as noted above.
 - Data collected via REDCap.
 - Time: < 3 minutes
 - Appendix G

All participants who enroll for the PT intervention will be randomized (1:1) into the LIFT subgroup or the LIFT + REAP subgroup at 2 weeks after enrollment/baseline session. The LIFT subgroup will continue to follow up as detailed above. The LIFT + REAP subgroup will undergo Realistic Effort Action Planning (REAP), which is described below:

LIFT + REAP subgroup:

Follow up:

- *REAP introduction (2 weeks after enrollment, via telephone/videoconference, time: 30 minutes)*
 - Performed by a member of the research team.

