 - Number of hospitalizations, intensive care unit admissions, duration of hospitalizations, duration of intensive care unit admission, development of decompensating events (ascites, hepatic encephalopathy, presence of esophageal/gastric varices, history of variceal bleeding, hepatorenal syndrome, hepatopulmonary syndrome, infections), transplant status, date of death, cause of death, placement on LT waitlist, delisting from LT waitlist, date of transplant, type of LT (living donor LT, simultaneous liver-kidney), duration of hospital admission for LT, duration of ICU admission for LT, duration of intubation post-LT, post-transplant discharge disposition, post-transplant complications (rejection, infection, biliary complications, hypertension, hyperlipidemia), liver frailty index scores, Karnofsky Performance Status Scores, body mass index (BMI), and laboratory data (platelets, serum sodium, serum creatinine, PT/INR, total bilirubin, albumin, calculated MELD).

DATA AND SPECIMEN BANKING

Data/specimens will not be banked for future use.

The data collected in this study will also be used in the Functional Assessment in Liver Transplantation study (STU00203582), The Role of Circadian Dysfunction in Hepatic Encephalopathy in Patients with Cirrhosis study (STU00204423), and the Personality, QOL and Frailty in Liver Transplantation study (STU00212668).

SHARING RESULTS WITH PARTICIPANTS

Study results will not be shared with participants or anyone else.

STUDY TIMELINES

Patients will be prospectively enrolled in the study from 9/13/2020 vs date of IRB approval to 7/31/2025. Patients in the Quality of Life Assessment arm will remain enrolled in the study while on the liver transplant waitlist and until 3 years after liver transplantation or up to a maximum of 5 years if not listed for liver transplantation. Patients in the PT Intervention arm will remain enrolled in the study while on the liver transplant waitlist and until 1 year after liver transplantation or up to a maximum of 5 years if not listed for liver transplantation. The estimated date for completion of primary analyses is 9/1/2025.

INCLUSION AND EXCLUSION CRITERIA

PT Intervention Study

Inclusion (criteria will be confirmed during consent process and during in-clinic physical therapy evaluation)

- Patients with a diagnosis of liver cirrhosis being evaluated for liver transplantation in hepatology/transplant evaluation clinic
- English-speaking

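### Primary analyses are due at most 32 days after enrolment closes, with no data cut-off, minimum follow-up or censoring rule, although PT participants are to be followed to 1 year after transplant

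*Combined protocol and SAP*

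**What the plan says.** Study Timelines gives three facts in one paragraph.

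- Enrolment: "Patients will be prospectively enrolled in the study from 9/13/2020 vs date of IRB approval to 7/31/2025".
- Follow-up in the PT Intervention arm: while on the waitlist and "until 1 year after liver transplantation or up to a maximum of 5 years if not listed for liver transplantation".
- Analysis: "The estimated date for completion of primary analyses is 9/1/2025".

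Study Endpoints makes LFI a primary endpoint. It also lists "Clinical outcomes: placement on LT waitlist, waitlist-mortality, post-transplant mortality, post-transplant disposition" as primary, together with the number and length of hospital stays and liver-related complications. None of these has an assessment time point.

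Procedures Involved places randomisation to LIFT or the "LIFT + REAP subgroup at 2 weeks after enrollment/baseline session". Home LFI is scheduled every 4 weeks and clinic LFI every 3 months.

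The Statistical analysis paragraph (under Data Management and Confidentiality) compares categorical clinical endpoints by chi-squared test and continuous ones by t-test, between LIFT and LIFT + REAP. It adds one sentence on a survival analysis adjusted for variables found significant in regression. No data cut-off, minimum follow-up, administrative censoring rule or later final analysis appears anywhere in the document.

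**The concern.** The analysis date follows the last permitted enrolment so closely that late enrolees contribute almost nothing to the primary endpoints, while the earliest could contribute nearly five years. For endpoints that accumulate with time, such as deaths, admissions, days in hospital and complications, a chi-squared or t-test gives both kinds of participant the same weight. A late enrolee without an event is counted like someone observed for years without one.

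The resulting proportions and mean counts describe no defined period. They cannot be read as risks at any time point. Nor can they be set against the retrospective control group, whose observation window differs: patients evaluated from 1/1/2018 to 10/26/2020, using only data already in the record at IRB submission.

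**Working it through.** **Inputs.** From Study Timelines: earliest stated enrolment 9/13/2020, last enrolment 7/31/2025, primary analyses complete 9/1/2025, PT follow-up to 1 year after transplant. From Procedures Involved: randomisation 2 weeks after enrolment, home LFI every 4 weeks, clinic visit every 3 months. The plan gives no derivation of 9/1/2025, so there is no calculation to reproduce.

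**Step 1. Gap from last enrolment to analysis.** 7/31/2025 to 9/1/2025 = 32 days. Because 9/1/2025 is when the analyses are to be finished, the data must be cut earlier, so 32 days is an upper bound.

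**Step 2. The last PT enrolee.**
- Randomised: 7/31/2025 + 14 days = 8/14/2025.
- Randomised time by 9/1/2025: 32 − 14 = 18 days.
- First 4-week home LFI, counted from enrolment: 7/31/2025 + 28 days = 8/28/2025. This is one measurement at most; counted from randomisation it falls on 9/11/2025, after the analysis date.
- First 3-month clinic visit: about 10/31/2025, after the analysis date.

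**Step 3. The post-transplant year.** One year before 9/1/2025 is 9/1/2024. Any PT participant transplanted after 9/1/2024 lacks the specified year, whatever the accrual pattern. If the last enrolee is transplanted after enrolling, that year cannot end before 7/31/2026.

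**Step 4. Spread of follow-up.** The earliest stated enrolee has 9/13/2020 to 9/1/2025 = 1,814 days (1,814 / 365.25 = 4.97 years). The last has 32. Both would enter the same test.

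**Step 5. Share affected.** The documents give no accrual pattern, so this step assumes uniform accrual over 9/13/2020 to 7/31/2025 = 1,782 days.

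| Shortfall at 9/1/2025 | Formula | Share |
|---|---|---|
| No 3-month visit (91 days) | (91 − 32) / 1,782 | 3.3% |
| Under 1 year since enrolment | (365 − 32) / 1,782 | 18.7% |

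Range: the start date is left open between 9/13/2020 and IRB approval. Starting instead at the end of the control window, 10/26/2020 (43 days later), the denominator is 1,739 and the shares become 59 / 1,739 = 3.4% and 333 / 1,739 = 19.1%. If accrual finished early, the shares fall: the first reaches zero if the last participant enrols by 6/2/2025, the second if by 9/1/2024. Accrual weighted to the end would raise them.

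**The case against.** The strongest reply is that a primary analysis may properly precede the end of follow-up. The plan says separately how long patients stay enrolled and when the analysis is estimated to be done; it never says the analysis waits for everyone to finish. That is right. A reader might infer that the dates and the follow-up periods flatly contradict each other, and the text does not go that far. What stands is that an analysis ahead of full follow-up needs a cut-off and a censoring rule, and neither is given.

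Other stronger readings also fail.

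- **That only proportions and means are planned.** A survival analysis is mentioned, and with proper censoring it could handle incomplete mortality follow-up. But the sentence names no endpoint, time origin or censoring rule, and it does not repair t-tests on admission counts or accumulated hospital days.
- **That nobody can reach five years, so follow-up fails.** Five years is a ceiling for patients never listed, not a required duration.
- **That the Quality of Life arm's follow-up shows the same shortfall.** Its period, "until 3 years after liver transplantation or up to a maximum of 5 years if not listed for liver transplantation", runs from transplant, and that arm admits patients already transplanted. Time since enrolment does not measure its completeness, and the arm is not part of the randomised comparison.
- **That the randomised comparison is biased.** Allocation is 1:1, so late enrolment should fall on both arms alike.
- **That a 1-year mortality endpoint is understated.** The endpoint has no time point; one year is only how long PT participants stay in the study. Discharge disposition is known early in any case.

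It is also fair that the LFI shortfall is small at the 3-month visit, and that the target of 500, which covers all groups, could be met before 7/31/2025.

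**Conclusion.** The point holds as a gap in the analysis timing. As written, primary analyses finish at most 32 days after the last permitted enrolment, and nothing states what follow-up each primary endpoint needs or how shorter follow-up is handled. The exact results rest on printed dates alone: 32 days, about 18 randomised days for the last PT enrolee, no 3-month clinic LFI for that participant, and no complete post-transplant year for anyone transplanted after 9/1/2024. The shares of 3.3% and 18.7% rest on uniform accrual to the last day.

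The harm is mainly lost information, plus event proportions and counts without a defined period, including in any comparison with the retrospective controls. It should be corrected before analysis. It does not by itself invalidate the comparison of LIFT with LIFT + REAP.

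**What to change.** Keep the enrolment window and restate the analysis date behind named data cut-offs.

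1. **LFI:** analyse after the last randomised participant's 3-month clinic visit, so not before about November 2025 if enrolment ends 7/31/2025.
2. **Clinical outcomes:** set a cut-off at least 1 year after last enrolment, so not before about 8/1/2026, and censor everyone still under observation at that date. The protocol names no time point, so the 3-month and 1-year minimums are proposals for the sponsor to confirm.
3. **Deaths and listing:** make the survival analysis already planned the primary analysis, with endpoint, time origin and censoring stated.
4. **Post-transplant mortality:** analyse as time-to-event from transplant, because 1 year from enrolment does not guarantee 1 year after transplant.
5. **Hospitalisations:** analyse as rates per person-time. For liver complications, name in advance a censored or exposure-adjusted method.

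Cost: protocol wording and no added procedures. Primary results come about 2 months later for LFI (9/1/2025 to November 2025) and about 11 months later for clinical outcomes (9/1/2025 to 8/1/2026). Some participants transplanted late will still have less than a post-transplant year at the cut-off; censoring handles them but does not recover their missing time.
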